11.1.2 Partial Response (PR)

Greater than or equal to 50% reduction in tumor size by bi-dimensional measurement, as compared with the baseline measurements, on a stable or decreasing dose of corticosteroids, accompanied by a stable or improving neurologic examination, and maintained for at least 8 weeks. If CSF was positive for malignant cells, it must be negative.

11.1.3 Stable Disease (SD)

Neurologic exam is at least stable and maintenance corticosteroid dose not increased, and MR/CT imaging meets neither the criteria for PR nor PD. CSF can be positive or negative for malignant cells. If this category is to be reported as of possible clinical benefit, Stable Disease status must be maintained for at least 4 courses.

11.1.4 Progressive Disease (PD)

Progressive Disease (PD): Progressive neurologic abnormalities or worsening neurologic status not explained by causes unrelated to tumor progression (e.g., anticonvulsant or corticosteroid toxicity, electrolyte disturbances, sepsis, hyperglycemia, etc.), OR a greater than 25% increase in the bi-dimensional measurement, taking as a reference the smallest disease measurement recorded since the start of protocol therapy, OR the appearance of a new lesion (including new appearance of malignant cells in the CSF), OR increasing doses of corticosteroids required to maintain stable neurological status or imaging.

12 DATA REPORTING/ REGULATORY REQUIREMENTS

Adverse event lists, guidelines, and instructions for AE reporting can be found in Section 7.

12.1 Data Reporting

12.1.1 Responsibility for Data Submission

Data collection for this study will be done exclusively through the Medidata Rave clinical data management system. Access to the trial in Rave is granted through the iMedidata application to all persons with the appropriate roles assigned in Regulatory Support System (RSS). To access Rave via iMedidata, the site user must have an active CTEP-IAM account (check at <<https://ctepcore.nci.nih.gov/iam>>) and the appropriate Rave role (Rave CRA, Read-Only, CRA (Lab Admin, SLA or Site Investigator) on either the LPO or participating organization roster at the enrolling site. To hold Rave CRA role or CRA Lab Admin role, the user must hold a minimum of an AP registration type. To hold the Rave Site Investigator role, the individual must be registered as an NPVR or IVR. Associates can hold read-only roles in Rave.

Upon initial site registration approval for the study in RSS, all persons with Rave roles assigned on the appropriate roster will be sent a study invitation e-mail from iMedidata. To accept the invitation, site users must log into the Select Login (<https://login.imedidata.com/selectlogin>) using their CTEP-IAM user name and password, and click on the “accept” link in the upper right-corner of the iMedidata page. Please note, site users will not be able to access the study in Rave until all required Medidata and study specific trainings are completed. Trainings will be in the form of electronic learnings (eLearnings), and can be accessed by clicking on the link in the upper right pane of the iMedidata screen.

Users that have not previously activated their iMedidata/Rave account at the time of initial site registration approval for the study in RSS will also receive a separate invitation from iMedidata to activate their account. Account activation instructions are located on the CTSU website, Rave tab under the Rave resource materials (Medidata Account Activation and Study Invitation Acceptance). Additional information on iMedidata/Rave is available on the CTSU members’ website under the Rave tab at www.ctsu.org/RAVE/ or by contacting the CTSU Help Desk at [name] or by e-mail at [contact].

Users may also contact OBDMC to get help with study specific issues including clinical forms, data entry, data query, data sign-offs and/or uploading of regulatory and other required documents. For complete OBDMC contact details, click on the OBDMC Contact Information link that is available in the Members’ Area of the PBTC website (<http://www.pbtc.org/>).

12.1.2 Method

This study will be monitored by the Clinical Data Update System (CDUS) Version 3.0. A protocol and subject-specific CDUS “Abbreviated” data set will be submitted electronically to CTEP on a quarterly basis via CDUS OPEN (Oncology Patient Enrollment Network). Reports are due January 31, April 30, July 31, and October 31. Instructions for submitting data using the CDUS can be found on the CTEP website (<http://ctep.cancer.gov/reporting/cdus.html>).

12.2 Collaborative Agreements Language

Not applicable.

12.3 Participant and Data Confidentiality

Participant confidentiality is strictly held in trust by the participating investigators, their staff and the sponsor(s) and their agents. This confidentiality is extended to cover testing of biological samples and genetic tests in addition to the clinical information relating to participants. Therefore, the study protocol, documentation, data and all other information generated will be held in strict confidence. No information concerning the study and the data will be released to an unauthorized third party without the prior written approval of the Pediatric Brain Tumor Consortium (PBTC).

The PBTC protocol coordinators, other authorized representatives of the sponsor, regulatory representatives, PBTC auditors, representatives of the IRB or the pharmaceutical collaborator supplying study product may inspect all documents and records required to be maintained by the investigator, including but not limited to, medical records (office, clinic, or hospital) and pharmacy records for the participants in this study. The clinical study site will permit access to such records.

Source documents which are the original records of clinical findings, observations or activities in a clinical trial are to be maintained at each participating site. Sites must upload all source documentation which supports the eligibility of the participant to the PBTC via the RAVE database. In the event the patient experiences unexpected events, additional source documentation may be requested to complete the event review. These documents may include but are not limited to, hospital records, clinical and office charts, laboratory notes, memoranda and radiographic images.

Study participant study related data, which is for purposes of statistical analysis and scientific reporting will be transmitted to the Pediatric Brain Tumor Consortium electronically via the RAVE database. This will not include the participant's contact or identifying information. Rather, research participants and their research data will be identified by a unique study identification number assigned at the time of screening or registration. The study participant's contact information will be securely stored at each clinical site for internal use during the study. At the end of the study, all records will continue to be kept in a secure location for as long a period as dictated by local IRB and institutional regulations.

The study data entry and study management systems used by clinical sites and by the PBTC will be secured and password protected. At the end of the study, all study data is maintained on a secure server.

After the study is completed, the data collected will be maintained on a server and may be used by other investigators, including those outside the study. With the participant's approval and as approved by local IRBs, biological samples labeled only with the participant's protocol specific identification number will be stored at the PBTC Central Review and Biorepository and could be made available to other investigators for future unspecified research. Investigators conducting future studies will not have access to the key for stored data collected while the participant is on study. Clinical data will be de-identified before it is shared with other investigators.

NCI Protocol#: PBTC-042
Version Date: 28 June 2018

If the participant agrees to submit a repository sample, those samples contain genetic information that may be used for research related to brain tumors and their treatment. They may also be used to develop tests/assays to improve diagnosis and treatment of these diseases in the future. Genetic research may consist of the analysis of one or more genes or the analysis of genetic markers throughout the genome.

13 STATISTICAL CONSIDERATIONS

13.1 Evaluability

13.1.1 Evaluability for DLT Assessment

Patients who receive at least one dose of the study drug and are taken off treatment for toxicity during the first course (dose-finding period) are evaluable for estimating the MTD. Similarly patients who have to go off treatment due to inability to de-escalate following toxicity because of BSA restrictions are also evaluable for DLT assessment and for estimating the MTD.

Patients who receive approximately 85% (17 or more doses) of prescribed therapy during the dose-finding period but who progress prior to completing the course may be considered evaluable for estimating the MTD, as long as no additional anti-cancer therapy or supportive care that would confound the interpretation of any observed toxicity or side effect is given. Patients must have completed all of the clinical and laboratory monitoring requirements specified by the protocol up to the time of disease progression for them to be considered evaluable for MTD.

Patients who have completed all therapy during the dose-finding period but who failed to comply with all the specified clinical and laboratory monitoring requirements for the first course will be considered inevaluable for estimating the MTD and replaced.

Patients who receive less than 17 doses of the protocol specified therapy and who go off treatment for reasons other than toxicity (e.g. progressive disease, withdrawal of consent etc.) during the dose finding period will be considered inevaluable for estimating the MTD and will be replaced. However as noted above, patients who go off treatment due to inability to de-escalate following toxicity as a result of BSA restrictions are evaluable.

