2.2.2.1 Animal Toxicity

Results of animal toxicity studies in this section have been obtained from the Investigator's Brochure and have not been published yet. Pivotal toxicity studies were performed in rats and dogs. The latter animal was chosen due to the drug's better bio-availability in this species than in non-human primates. The predominant toxicities were related to bone marrow, lymphoid, and testicular tissues. In the pivotal 3-week toxicity study, deaths occurred at a dose of 1200 mg/m² and 2400 mg/m² given once daily for 3 weeks in male and female rats respectively. Death occurred in dogs at > 200 mg/m² daily for 2 weeks. Reversible bone marrow suppression (especially neutropenia) and lymphoid depletion (mesenteric lymph node, spleen, and thymus)

were observed in rats (males > females) at doses of > 300-1200 mg/m². Decrease in reticulocytes, neutrophils, and monocytes were observed within one week of treatment with variable nadir times and recovery within 2 weeks of cessation of therapy. In dogs, similar changes were observed at doses > 12mg/m² and nadir time was typically seen at the end of the dosing period (day 21).

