5.1.1 Dose-finding Period

The dose finding period begins with the initial dose of PD-0332991 (IBRANCE) and ends on the last day of course 1. Should there be a delay starting the subsequent course, dose finding will complete on the start date of the subsequent course.

Dose escalations will be based on toxicities observed during the dose finding period.

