5.1.2 Dose Escalation Schedule

The pediatric equivalent of the adult MTD for the once daily administration of PD-0332991 (IBRANCE) based on a 3-week on/1 week off schedule is approximately 75mg/m². PD-0332991 (IBRANCE) dosing will begin at 50 mg/m². The PD-0332991 (IBRANCE) dose will be increased in subsequent cohorts until the MTD is reached ([Table 7](#)) or the highest proposed dose is determined to be safe.

The

[Table 7](#) below lists the proposed dose levels to be studied along with the BSA restrictions for each dose level for both Strata I and II. At the time of submission of version 8.0, a total of 21 patients had been enrolled in stratum I. No DLTs were observed in 3 patients enrolled in dose

level 1 and 6 patients enrolled in dose level 2. At dose level 3, a total of 6 patients were enrolled and 2 were inevaluable for toxicity assessment. Two of 4 evaluable patients at this dose level experienced DLTs (grade 4 neutropenia); hence the MTD was exceeded at dose level 3. The MTD for stratum I was determined as dose level 2 (75 mg/m²/day) and this stratum has been closed to accrual.

The starting dose level for stratum II is one dose level below the stratum I MTD (i.e. 50 mg/m²/day). If this dose is well tolerated in the initial cohort of patients enrolled on Stratum II, the dose will be escalated to 75 mg/m²/day for the next cohort of patients. No further escalation will be allowed in this stratum.

[figure not shown]
The plot below the table demonstrates that dosing using the available capsule sizes is feasible for the proposed dose levels using the BSA restrictions outlined in the table below. It is not however possible to include a level below 50mg/m²/day due to the capsule size limitations. No intra-patient dose escalation will be permitted on the protocol. Only DLTs observed during the dose-finding period will be used to guide dose escalation. Dose escalation will be governed by the Rolling-6 statistical design separately in each of the two strata, as described in section [13.2](#) of the protocol.

Table 7
Stratum I and II: PD-0332991 (IBRANCE) Dosing Regimen and BSA Restrictions

Dose Level	Dose (mg/m ²)	BSA (m ²)
1*	50	≥ 1.20
2**	75	≥ 0.93
3	95	≥ 0.70

* Starting dose for Stratum II

** MTD for stratum I

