5.2.1 The following are Dose-Limiting Toxicities (DLT's)

- A PD-0332991 (IBRANCE) related adverse event will be considered dose-limiting if it leads to a dose reduction or permanent cessation of treatment during the first course of therapy. All dose modifications in all courses are to follow the guidelines provided in section 6.2.

- Inability to receive the next cycle of PD-0332991 (IBRANCE) within two weeks of the last dose because of lack of hematologic recovery or persisting non-hematologic toxicity.

5.2.1.1 Non-hematologic dose limiting toxicity is defined as:

- Any grade 4 non-hematologic toxicity
- Any grade 3 non-hematologic toxicity with the exception of:
 - Grade 3 nausea and vomiting of < 5 days
 - Grade 3 diarrhea and/or electrolyte disturbances which have not been maximally treated
 - Grade 3 AST/ALT elevation that returns to levels meeting eligibility criteria within 7 days of study drug interruption and does not recur upon restarting drug.
- Any Grade 2 non-hematologic toxicity that persists for > 7 days and is considered medically significant or sufficiently intolerable by patients requires treatment interruption.

5.2.1.2 Hematologic dose limiting toxicity is defined as:

- Grade 3 neutropenia with fever and sepsis
- Any Grade 4 hematologic toxicity with the exception of lymphopenia
- Grade 3 thrombocytopenia and/or requiring a platelet transfusion on 2 separate days within a 7-day period

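### Section 13.1.1 does not say that a patient with an observed DLT is always evaluable, so a DLT can be discarded and the patient replaced, chiefly when course-1 monitoring was missed

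*Combined protocol and SAP*

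**What the plan says.** **Evaluability (13.1.1).** Four rules matter here.

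1. Patients given at least one dose who "are taken off treatment for toxicity during the first course (dose-finding period) are evaluable for estimating the MTD". Patients who must stop because BSA prevents de-escalation after toxicity are evaluable too.
2. Patients with 17 or more doses who then progress may be evaluable if no confounding therapy or supportive care was given. In addition, "Patients must have completed all of the clinical and laboratory monitoring requirements specified by the protocol up to the time of disease progression".
3. Patients who finished all therapy in the dose-finding period but "failed to comply with all the specified clinical and laboratory monitoring requirements for the first course will be considered inevaluable for estimating the MTD" and are replaced.
4. "Patients who receive less than 17 doses of the protocol specified therapy and who go off treatment for reasons other than toxicity" in the dose-finding period are inevaluable and replaced.

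**DLT and its window.** Section 5.2.1 lists as a DLT "Inability to receive the next cycle of PD-0332991 (IBRANCE) within two weeks of the last dose because of lack of hematologic recovery"; the same applies when the cause is non-hematologic toxicity that has not resolved. Section 5.1.1 runs the dose-finding period from the first dose to the last day of course 1 and adds: "Should there be a delay starting the subsequent course, dose finding will complete on the start date of the subsequent course".

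**Decision rule.** Section 5.1.2 says "Only DLTs observed during the dose-finding period will be used to guide dose escalation". In section 13.2 the escalation clause counts evaluable patients (none of 3 to 6, or at most 1 of 6). The clause declaring a dose too toxic at two DLTs does not use that word, and the decision table counts patients enrolled.

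**After a DLT.** For dose-limiting grade 3 or 4 events, Table 8 (section 6.2) holds drug. It allows restart one level down for level 2 or 3 patients who meet the lower level's BSA limit, and takes level 1 patients off permanently. Section 5.5.2 lists toxicity as outlined in 5.2.1 among the reasons for coming off treatment.

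**The concern.** Evaluability conditions exist so that a patient who was not adequately observed is not counted as free of DLT. Once a DLT has been seen, missed assessments cannot undo it. Rules 2 to 4 nevertheless apply the same conditions to patients with and without a DLT, and nothing says that rule 1 takes precedence.

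The MTD is a primary objective, and two DLTs in up to six patients settle the decision. In Stratum II, a discarded DLT at level 1 could lead to escalation in heavily pretreated children. At level 2, the highest level allowed in that stratum, it could lead to acceptance of that dose. As of version 8.0, four Stratum II patients were enrolled, all at level 1, so most of that stratum's decisions were still to come.

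**Working it through.** **Plan figures.** With the day 2 dose held for pharmacokinetics (9.2.2.1), course 1 has 21 − 1 = 20 planned doses, and 17/20 = 85%, as 13.1.1 states. The Stratum II maximum is 2 levels × 6 + 6 expansion = 18, as 13.3 states.

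**Who can fall through**

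- *Level 2, BSA at least 1.20, DLT first seen after the last dose of course 1.* All course-1 therapy is complete. Table 8 allows restart at the lower level, so the patient need not come off treatment and rule 1 need not apply. One missed assessment then brings in rule 3.
- *Level 2, BSA 0.93 to below 1.20.* The patient comes off treatment, so rule 1 applies.
- *Level 1, grade 3 or 4 DLT during dosing.* Table 8 removes the patient, therapy was not completed, and rule 1 applies.
- *Level 1, DLT in the rest week with an assessment missed.* Therapy is complete and the patient is removed for toxicity. Rules 1 and 3 both fit and give opposite answers.
- *Delayed recovery.* If the last dose is on day 21, this DLT is established at day 21 + 14 = 35, after the 28-day course. Section 5.1.1 then ends the period at the start of course 2, and gives no end if course 2 never starts.
- *Lesser routes.* A DLT followed by a non-toxicity exit with fewer than 17 doses (rule 4), or by progression after 17 or more doses with monitoring missed (rule 2).

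**Effect on one decision.** Seven patients are treated and two have a DLT, one of whom missed a required assessment. Under rule 3 there are six evaluable patients with one DLT, so the escalation clause is met. If every observed DLT counts, there are two, and the dose is too toxic.

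**Average effect (illustration).** Let p be the true DLT rate, q0 the share of non-DLT patients classed inevaluable, and q1 the share of DLT patients classed inevaluable after allowing for rule 1. The documents give none of these; all are assumptions.

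- Counted rate under the current rule: r = p(1 − q1) / [p(1 − q1) + (1 − p)(1 − q0)]
- Counted rate if every DLT counts: the same with q1 = 0
- Acceptance at six patients: (1 − r)^6 + 6r(1 − r)^5

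At p = 0.33:

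| Case | r | At most 1 DLT in 6 |
|---|---|---|
| No loss | 33.0% | 35.8% |
| q0 = 10%, every DLT counts | 35.4% | 31.2% |
| q0 = 10%, q1 = 7.5% | 33.6% | 34.6% |
| q0 = 10%, q1 = 10% | 33.0% | 35.8% |
| q0 = 10%, q1 = 15% | 31.7% | 38.3% |

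For example, with q1 = 15%: r = 0.33 × 0.85 / (0.33 × 0.85 + 0.67 × 0.90) = 0.2805 / 0.8835 = 0.317. Acceptance exceeds the no-loss value only when q1 > q0.

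For escalation from level 1, with three patients assessed first and then up to six, P = (1 − r)^3 + 3r(1 − r)^5. At p = 0.33 this is 43.4% with no loss. With q0 = 10% it is 42.3% at q1 = 7.5% and 39.0% at q1 = 0.

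**Cost of counting every DLT.** At p = 0.20 and q0 = 10%, r = 0.20 / (0.20 + 0.80 × 0.90) = 21.7%. Acceptance at six falls from 65.5% with no loss to 61.3%.

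**The case against.** The case for leaving the text alone has real force.

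- Rule 3 covers only patients who completed all therapy. Table 8 holds drug for dose-limiting grade 3 and 4 events, so most DLTs during dosing fall outside it. This stands and narrows the reach.
- Level 1, the only Stratum II level with patients at version 8.0, is largely protected by removal for toxicity. This stands.
- Read literally, 5.5.2 takes every DLT patient off treatment, so rule 1 would protect them all, including at level 2. But Table 8 says otherwise, and a patient removed in the rest week would still fit rule 3 as well.
- If course 2 never starts, the dose-finding period could be read as still open, which favors counting a delayed-recovery DLT. That is a fair reading, but it is not stated.
- Much of 13.2, and 5.1.2, point to counting every DLT. This stands too, but the escalation clause counts evaluable patients, and nothing says which text governs.

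A reader might infer from the dog data in 2.2.2.1 that DLTs are to be expected after the last dose. They do not show this: the reported nadir, day 21, is itself the last dosing day. Late DLTs are possible under the definition in 5.2.1; their frequency is not documented.

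A reader might also infer that the rule biases the MTD upward. That needs DLT patients to be lost more often than non-DLT patients, which the documents do not establish. Blood counts become more frequent after a DLT, and a laboratory DLT is seen only if the test was done.

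**Conclusion.** The gap is real and should be fixed. As written, 13.1.1 can discard an observed DLT, and one discarded DLT can reverse a dose decision. The clearest exposure is a DLT after the last dose at Stratum II level 2 with BSA of at least 1.20. At level 1 what remains is the clash of rules 1 and 3 and the open-ended window for delayed recovery.

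The size and direction of any average bias are unknown. Equal loss gives no inflation. If few DLT patients are unprotected, as is plausible at level 1, the current rule is no more permissive than no loss. The percentages illustrate assumed loss rates and are not expected effects.

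Nor do the documents show that a DLT has been discarded. They give no reason for the two inevaluable Stratum I level 3 patients, and that level was declared too toxic regardless. The six-patient expansion (13.2) and safety tables on everyone dosed (13.4) limit the consequences. However, the expansion has no numeric trigger, and the tables do not drive escalation.

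**What to change.** Place first in 13.1.1: *Any patient who receives at least one dose and has a DLT during the dose-finding period is evaluable and counts as a DLT, regardless of doses received, missed monitoring, supportive care or later reason for going off treatment.* Apply the dose, monitoring and supportive-care conditions only to patients without a DLT.

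Align the replacement sentence in 5.2 and the counting language in 13.2 with this. State in 5.1.1 when the dose-finding period ends for a patient who never starts course 2. Sections 5.5.2 and 6.2 (Table 8) disagree on whether a patient with a 5.2.1 toxicity may restart; the sponsor must reconcile them.

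The cost is a few sentences and no added procedures. The rule is slightly conservative, because patients without a DLT can still drop out of the count: with 10% of them lost, a true 33% is counted as 35.4%, and a tolerable dose at a true 20% is accepted a little less often, as worked above.
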